5.3.7.2 Post-Treatment Review

Within one week of the completion of radiotherapy, the following data shall be submitted.

- A copy of the patient's radiotherapy record including prescription, and the daily and cumulative doses to all required areas and specified dose points.
- Copies of additional simulation and verification (portal) films for any field modifications made subsequent to the initial reporting of data for on-treatment review.
- Copies of revised RT-1/IMRT form, when modifications have been made subsequent to the initial reporting.
- Copies of calculations and isodoses performed subsequent to the submission of the on-treatment data.

- Copy of the ECOG-ACRIN E2108 Checklist for Submission of Radiation Oncology Quality Assurance Materials (located at www.QARC.org).

NOTE: Black and white copies of color documentation are not acceptable.

5.3.9 Definitions of Deviations in Protocol Performance

5.3.9.1 Prescription Dose

Minor Deviation: The dose to the prescription isodose surface differs from that in the protocol by between 6% and 10%.

Major Deviation: The dose to the prescription isodose surface differs from that in the protocol by more than 10%.

5.3.9.2 Dose Uniformity

Fluoroscopy based (2D) Treatment Planning: The dose variation on an axial contour through the center of the target volume is greater than -5% or +15% of the protocol dose.

3D/IMRT Treatment Planning: Any part of the CTV receives less than 95% of the protocol dose, or more than

10% of the PTV receives more than 110% of the protocol dose.

5.3.9.3 Volume

Minor Deviation: Margins less than specified or fields excessively large as deemed by the study.

Major Deviation: Transection of tumor or potentially tumor bearing area (CTV).

Rev. 7/12

5.4 Adverse Event Reporting Requirements

Step 1: Identify the type of event: The descriptions and grading scales found in the revised NCI Common Terminology Criteria for Adverse Events (CTCAE) version 4.0 will be utilized. All appropriate treatment areas should have access to a copy of the CTCAE version 4.0. A copy of the CTCAE version 4.0 can be downloaded from the CTEP web site (<http://ctep.cancer.gov>).

Step 2: Grade the event using the NCI CTCAE v 4.0.

Rev. 7/12

5.4.1 Reporting Methods

This study requires that expedited adverse event reporting use CTEP's Adverse Event Reporting System (CTEP-AERS). CTEP's guidelines for CTEP-AERS can be found at <http://ctep.cancer.gov>. A CTEP-AERS report must be submitted electronically to ECOG-ACRIN and the appropriate regulatory agencies via the CTEP-AERS Web-based application located at <http://ctep.cancer.gov>.

In the rare event when Internet connectivity is disrupted a 24-hour notification is to be made by telephone to

- the AE Team at ECOG-ACRIN [contact])
- the NCI [contact])

An electronic report **MUST** be submitted immediately upon re-establishment of internet connection.

Supporting and follow up data: Any supporting or follow up documentation **must be faxed** to ECOG-ACRIN [contact]), Attention: AE within 48-72 hours. In addition, supporting or follow up documentation must be faxed to the NCI ([name]) in the same timeframe.

NCI Technical Help Desk: For any technical questions or system problems regarding the use of the CTEP-AERS application, please contact the NCI Technical Help Desk at [contact] or by phone at [name].

5.4.2 Other Recipients of Adverse Event Reports

ECOG-ACRIN will forward CTEP-AERS reports to the appropriate regulatory agencies and pharmaceutical company, if applicable.

Adverse events determined to be reportable must also be reported by the institution, according to the local policy and procedures, to the Institutional Review Board responsible for oversight of the patient.

5.4.3 Expedited Reporting for Protocol E2108 – Arms A and B

Attribution			Grade 5 ^a		
			Unexpected	Expected	
Possible, Probable, Definite			7 calendar days	7 calendar days	
7 Calendar Days: Indicates a full CTEP-AERS report is to be submitted within 7 calendar days of learning of the event.					

a This includes all deaths within 30 days of the last dose of treatment regardless of attribution.
 
NOTE: Any death on either arm that occurs > 30 days after the last dose of treatment and is attributed possibly, probably, or definitely to the treatment must be reported within 7 calendar days of learning of the event.
					

Rev. 7/12

5.4.4 Reporting secondary primary cancers

All cases of second primary cancers, including acute myeloid leukemia (AML) and myelodysplastic syndrome (MDS), that occur following treatment on NCI-sponsored trials must be reported to ECOG-ACRIN:

- **A second malignancy is a cancer that is UNRELATED to any prior anti-cancer treatment (including the treatment on this protocol). Second malignancies require ONLY routine reporting as follows:**
 1. Submit a completed Second Primary Form within 30 days to ECOG-ACRIN at
ECOG-ACRIN Operations Office - Boston
FSTRF
[name]
[name]
 2. Submit a copy of the pathology report to ECOG-ACRIN confirming the diagnosis
 3. If the patient has been diagnosed with AML/MDS, submit a copy of the cytogenetics report (if available) to ECOG-ACRIN
- **A secondary malignancy is a cancer CAUSED BY any prior anti-cancer treatment (including the treatment on this protocol). Secondary malignancies require both routine and expedited reporting as follows:**
 1. Submit a completed Second Primary Form within 30 days to ECOG-ACRIN at
ECOG-ACRIN Operations Office - Boston
FSTRF
[name]
[name]
 2. Report the diagnosis via CTEP-AERS at
<http://ctep.cancer.gov>
Report under a.) leukemia secondary to oncology chemotherapy, b.) myelodysplastic syndrome, or c.) treatment related secondary malignancy

3. Submit a copy of the pathology report to ECOG-ACRIN and NCI/CTEP confirming the diagnosis.
4. If the patient has been diagnosed with AML/MDS, submit a copy of the cytogenetics report (if available) to ECOG-ACRIN and NCI/CTEP.

NOTE: The Second Primary Form and the CTEP-AERS report should not be used to report recurrence or development of metastatic disease.

NOTE: If a patient has been enrolled in more than one NCI-sponsored study, the Second Primary Form must be submitted for the most recent trial. ECOG-ACRIN must be provided with a copy of the form and the associated pathology report and cytogenetics report (if available) even if ECOG-ACRIN was not the patient's most recent trial.

NOTE: Once data regarding survival and remission status are no longer required by the protocol, no follow-up data should be submitted via CTEP-AERS or by the Second Primary Form.

5.5 Supportive Care

5.5.1 All supportive measures consistent with optimal patient care will be given throughout the study. Growth factor support while on cytotoxic chemotherapy is allowed at the discretion of the treating physician.

5.6 Duration of Study Participation

All patients will be followed until progression and for survival. Those randomized to Early Local Therapy will receive protocol-specified surgery and radiation immediately after randomization. Study participation will continue for 5 years unless:

- 5.6.1 Patient withdraws consent.
- 5.6.2 Death.

6. Measurement of Effect

6.1 Response to Optimal Systemic Therapy on Step 1

Rev. 2/13

6.1.1 To be randomized, patients must not have experienced disease progression since the start of systemic therapy, as evidenced by clinical and radiographic documentation of disease status at baseline (see [3.1.4](#) for definition of baseline evaluation) compared to equivalent tests performed within 6 weeks prior to randomization, including:

- 6.1.1.1 No new sites of disease
- 6.1.1.2 No enlargement of existing sites by 20% or more (sum of the longest diameter of measurable lesions)
- 6.1.1.3 No symptomatic deterioration, defined as a global deterioration of health status requiring discontinuation of treatment without objective evidence of disease progression. Women whose loco-regional disease remains symptomatic at the end of induction therapy (i.e. ulcerations, skin nodules or pain from replacement of the breast with tumor or chest wall invasion) so that they require immediate local therapy for palliation are classified as having symptomatic deterioration and will not be randomized. They will be followed for survival.

6.2 Changes in Disease Status on Step 2

6.2.1 Local/Regional Assessment

The breast as well as cervical, supraclavicular, infraclavicular and axillary lymph nodes and chest wall disease must be assessed.

Breast evaluation will consist of:

- a) physical examination with complete documentation of the following: tumor in two longest dimensions; skin invasion (yes/no) skin ulceration (yes/no); tumor mobility (free/attached to fascia/chest wall fixation).
- b) Breast imaging studies with mammogram OR ultrasound OR breast MRI measurement are requested at baseline (see [3.1.4](#) and [7.1](#) for definition of baseline evaluation). However, if in the judgment of the physician, physical exam provides sufficient documentation of tumor size and T stage, and breast imaging has not been performed in the baseline period, the patient is still eligible. Preferably, the same imaging studies should be repeated in the pre-randomization interval (within 6 weeks prior to randomization). If the same study cannot be repeated (e.g. insurance denial of MRI), an equivalent study (e.g. mammogram or ultrasound) may be performed.
- c) [Deleted in Addendum #2]
- d) nodal evaluation and documentation of nodal involvement by physical examination is required

Rev. 7/12, 2/13

Rev. 7/13

Rev. 7/12

Rev. 4/14

- e) documentation of chest wall disease: if skin nodules are present, the sum of the longest diameter of the largest five nodules should be recorded. If ulceration is present, this should be recorded (yes/no) and the area of ulceration measured in cm.

6.3 Endpoints

- 6.3.1 Local Regional Recurrence (among patients randomized to Arm B)
The new development or clinically significant increase in size of any supraclavicular, infraclavicular, internal mammary or axillary adenopathy or chest wall disease or invasive in-breast recurrence
- 6.3.2 Local/Regional Progression (among patients randomized to Arm A)
The development of symptoms leading to a decision for local therapy.
- 6.3.3 Uncontrolled Chest Wall Disease
Clinical or radiological evidence of local tumor on the chest wall or the presence of skin involvement, ulceration, or symptoms.
- 6.3.4 Distant Progression
The development of new sites of non-local/regional metastatic disease or clinically significant increase in the size of existing lesions.
- 6.3.5 Survival
Date of randomization to date of death.
- 6.3.6 Quality of Life
Quality of life endpoints will be measured using patient-reported outcomes questionnaires. Domains to be assessed and instruments to be administered include FACT-G physical and functional well-being (FACT-B TOI), and domains specific to breast cancer (FACT Breast cancer subscale).

7. Study Parameters

7.1 Therapeutic Parameters

Rev. 2/13

1. Prestudy scans and x-rays used to assess all measurable or non-measurable sites of disease must be done **≤ 8 weeks** prior to the initiation of systemic therapy. If pre-therapy scans were not performed, scans performed within the first 4 weeks of systemic therapy will be accepted. The same window applies to history and physical, Local/Regional assessment, ECOG PS, weight and height.
2. Step 2 CBC (with differential and platelet count) must be done during the **6 weeks** preceding randomization.
3. All required Step 2 chemistries must be done **6 weeks** preceding randomization.
4. Step 2 scans and x-rays used to assess all measurable or non-measurable sites of disease must be done within the **6 weeks** preceding randomization. The same window applies to history and physical, Local/Regional assessment, ECOG PS, weight.

Rev. 4/14

Rev. 7/12,
2/13

Rev. 4/14

Rev. 7/12,
2/13

Rev. 7/12,
2/13, 4/14

	Step 1: Registration	Step 2: At randomization	6 months post randomization	12 months post randomization	18 months post randomization	30 months post randomization	At decision for local therapy (Arm A) ³	Long-Term followup ⁵
History & Physical	X ¹	X ⁴	X ¹²	X ¹²	X ¹²	X ¹²	X ⁴	Q 3 months years 0-2; Q 6 months years 2-5
Local/Regional ¹² Assessment	X ^{1,8}	X ⁴	X ¹²	X ¹²	X ¹²	X ¹²	X ⁴	
ECOG PS ¹²	X ¹	X ⁴	X ¹²		X		X ⁴	
Weight	X ¹	X ⁴	X ¹²		X		X ⁴	
Height ¹²	X ¹							
CT chest/abdomen ^{1,10}	X	X	X		X	X	X ⁴	
Bone scan ^{1,10}	X	X	X		X		X ⁴	
Mammogram ⁹	X	X			X		X ⁴	
Breast Ultrasound ⁹	X	X			X		X	
Pregnancy Test ²	X	X						
QOL assessment ¹¹	X ⁴	X ⁷	X		X	X	X	
CTC Enumeration ⁶		X ⁷	X					
Biological Sample Submissions								See Section 7.2

Rev. 7/12,
2/13

Rev. 4/14

Rev. 7/12

1. CT scans with bone windows or PET CT are allowed instead of CT chest/abdomen and bone scan. If performed at baseline, should be repeated within 6 weeks prior to randomization and during follow-up, if possible. If not possible (e.g. denied by insurance), other appropriate tests can be substituted that will evaluate all prior sites of disease and will address any new signs/symptoms.
2. Urine or serum pregnancy test must be done in women of child-bearing potential < 2 weeks prior to randomization.

Rev. 7/12 3. In Arm A patients, if a decision is made to deliver palliative local therapy, a complete local-regional assessment must document reason for palliative treatment and must include same imaging tests that were performed at start of systemic therapy, if possible. If not possible, (e.g. denied by insurance), other appropriate tests can be substituted that will evaluate all prior sites of disease and will address any new signs/symptoms.

Rev. 4/14 4. [Deleted in Addendum #2]

Rev. 7/12 5. Patients who are not randomized will be followed for survival for 5 years post registration.

Rev. 7/12 6. Collect only if performed as part of standard clinical assessments and covered by third party reimbursement.

Rev. 7/12, 7/13 7. Collect prior to randomization.

Rev. 4/14 8. Pathology reports confirming diagnosis of breast cancer and, if only one metastatic lesion is present, the metastatic site must be submitted to the ECOG-ACRIN Operations Office - Boston within one month of registration to step 1.

Rev. 4/14 9. Breast imaging studies with mammogram OR ultrasound OR breast MRI measurement are requested at baseline (see 3.1.4 and 7.1 for definition of baseline evaluation). However, if in the judgment of the physician, physical exam provides sufficient documentation of tumor size and T stage, and breast imaging has not been performed in the baseline period, the patient is still eligible. If possible, the same imaging studies should be repeated in the pre-randomization interval (within 6 weeks prior to randomization). If not possible (e.g. denied by insurance), other tests can be substituted that will evaluate the breast and will address any new signs/symptoms. Mammogram and ultrasound may be unilateral (affected side) or bilateral, at physician discretion. Breast imaging is not required if the breast is replaced by tumor or ulcerated in a way that makes breast imaging not feasible. If so, physical exam documentation must reflect this. A physical exam can only be used for pre-randomization evaluation of the breast if imaging is not feasible and tumor is palpable: in this case, physical exam findings describing the tumor must be documented. During follow-up breast imaging studies with mammogram OR ultrasound OR MRI need to be performed.

Rev. 4/14 10. If the patient is being registered >4 weeks after initiation of systemic therapy, and the test was not performed within the baseline window (8 weeks before to 4 weeks after start of systemic therapy), physician may declare (if appropriate) that test was not indicated, and the patient may still be registered.

Rev. 4/14 11. Window is +/- 14 days for each QOL administration time point (**except step 2 randomization**).

Rev. 4/14 12. Window is \pm 14 days.

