2.2 Secondary Objectives

Rev. 4/14

- 2.2.1 To compare the time to uncontrolled chest wall disease between patients who receive early local therapy versus patients who receive palliative local therapy
- 2.2.2 To determine whether there is a difference in HRQL between patients who receive early local therapy and those who receive palliative local therapy.
- 2.2.3 To determine whether the absolute value of the CTC burden at six months following randomization will be lower in Arm B than Arm A and whether this value is inversely related to survival.
- 2.2.4 To collect tumor and blood specimens for future exploration of the biological interactions between the primary tumor and metastatic lesions and the effect of primary tumor resection.

3. Selection of Patients

Each of the criteria in the checklist that follows must be met in order for a patient to be considered eligible for this study. Use the checklist to confirm a patient's eligibility. For each patient, this checklist must be photocopied, completed and maintained in the patient's chart.

In calculating days of tests and measurements, the day a test or measurement is done is considered Day 0. Therefore, if a test is done on a Monday, the Monday four weeks later would be considered Day 28.

ECOG-ACRIN Patient No. _____

Patient's Initials (L, F, M) _____

Physician Signature and Date _____

NOTE: All questions regarding eligibility should be directed to the study chair or study chair liaison.

NOTE: Institutions may use the eligibility checklist as source documentation if it has been reviewed, signed, and dated prior to randomization by the treating physician.

Rev. 7/12 **NOTE:** Patients may register (Step 1) at any time from the time of diagnosis of stage IV breast cancer (if eligibility criteria met) to the time when a maximum of 30 weeks of induction systemic therapy has been completed. (Induction systemic therapy includes chemotherapy, endocrine therapy, bone-specific agents, and biologic therapy.)

Rev. 7/13 **NOTE:** Patients must be randomized (Step 2) within 32 weeks after the start of systemic therapy.

Rev. 7/12 **NOTE:** Patients may not be randomized (Step 2) less than 16 weeks after the start of systemic therapy.

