8.4 Sample Size

The primary comparison will be an intention-to-treat analysis including all randomized patients. It is expected that the three-year survival in the control arm will be 30%. The primary analysis of survival will be performed using a one-sided logrank test stratified on the stratification factors including marker status and treatment plan, number of involved organ systems, using an overall type I error of 5%. Allowing for the interim analysis plan discussed below, a total accrual of 186 responders and a total information of 110 deaths is planned, to give 85% power

to detect a 19.3% difference in the three-year survival rates (i.e., 49.3 % in the experimental arm). To allow for 15% probability of crossover between two arms (sum of the probabilities of patients on the experimental arm crossing over to the control arm and vice versa), both numbers are inflated by a factor of 1.38 (based on the Lachin-Foulkes correction)(53) to a total accrual of 258 responders and a total information of 152 deaths. Assuming an exponential distribution, this difference corresponds to an improvement in median survival from 21.4 to 33.5 months. Assuming 70% of the recruited patients are eligible and responding, a total of 368 patients will be needed to accrue 258 responders. Assuming an accrual rate of 6 patients per month, 62 months of accrual will be needed. The sample size was computed using seqopr6 (part of the study design library at the ECOG-ACRIN Statistical Office).

Rev. 7/13, 4/14

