Rev. 7/13		Two sample t-test/Wilcoxon test will be conducted to test whether the CTC burden at 6 months after randomization will be lower in Arm B than in Arm A. Cox proportional hazards (PH) model will be used to examine whether patients with lower CTC burden at 6 months after randomization have prolonged survival. The treatment assignment, CTC burden or possibly their interaction will be included in the Cox PH model.
Rev. 7/13		Assuming 60% of the patients would provide their CTC at 6 months after randomization, we would have 155 evaluable patients, with 77 patients per arm. Assuming the standardized difference is 0.339 (difference in mean/standard deviation; e.g. the difference in CTC at 6 months after randomization for the two arms is 1 and the SD is 3), then the given sample size will provide 77% power using a two sample t test with two-sided significance level of 0.20.
Rev. 7/13		A paired t-test/ Wilcoxon test would be used to test whether there is a reduction in CTC burden from randomization to 6 month assessments in Arm B. A Cox PH model will be conducted to evaluate whether a larger reduction in CTC predicts longer survival.
		A two sample t-test/Wilcoxon test would be used to test whether the reduction in CTC in Arm B is larger than Arm A. A Cox PH model will be used to evaluate whether a larger reduction predicts longer survival.

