9.1.2.2 Collection and Shipping Kits

Kits will include vacutainers and cryovials for the aliquots of the serum and plasma.

Baseline kits must be requested within 48 hours (two business days) following registration. All other kits must be

requested at least 48 hours prior to scheduled use. You will need to request kits at each time point.

Complete the E2108 Collection and Shipping Kit Order Form, [Appendix VI](#) and Fax to Zemotak – International at [contact].

Rev. 7/12

Kits will be shipped overnight on the next working day and will include collection and shipping materials, and instructions for processing.

Questions regarding kits should be directed to Zemotak - International at [contact].

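### Circulating tumor cell counts are recorded only when done as reimbursed standard care, yet Section 8.7 compares the arms with an unweighted test on whoever has a 6-month value

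*Combined protocol and SAP*

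**What the plan says.** Objective 2.2.3 is "To determine whether the absolute value of the CTC burden at six months following randomization will be lower in Arm B than Arm A", and also asks whether the value relates to survival. Section 1.7 presents this 6-month contrast as sounder than a before-and-after comparison within Arm B.

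The 7.1 schedule has one row for "CTC Enumeration", at randomization and at 6 months. Its footnote 6 reads "Collect only if performed as part of standard clinical assessments and covered by third party reimbursement". Footnote 7 adds that the randomization sample is taken before randomization.

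Study blood (7.2 and 9.1.2) consists of serum, EDTA plasma with residual cells, and a DNA tube, all for banking. On the kits, 9.1.2.2 says "Kits will include vacutainers and cryovials for the aliquots of the serum and plasma". No tube, laboratory or assay is assigned to CTC counting.

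Section 8.7 states: "Assuming 60% of the patients would provide their CTC at 6 months after randomization, we would have 155 evaluable patients". It gives no source for the 60%. It plans a two-sample t or Wilcoxon test at 6 months, paired and between-arm tests of the reduction from randomization, and Cox models. Section 8.6 provides a joint model for informative missingness, but only for quality of life. Section 8.7 has no counterpart.

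**The concern.** Randomization makes the arms comparable as randomized. It does not make comparable the subset for whom someone ordered a test after randomization and a payer covered it. The trial is unblinded: by 6 months most Arm B patients should have had surgery, while most Arm A patients still have the primary tumor in place. If a count is more likely to be ordered for a worsening patient in one arm than in the other, the tested patients will differ in CTC burden even if local therapy does nothing. A plain two-sample test cannot tell that difference from a treatment effect. At stake is the arm comparison in objective 2.2.3. The overall survival analysis uses all randomized patients and is untouched.

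**Working it through.** **1. The plan's own figures.** Inputs: "a total accrual of 258 responders and a total information of 152 deaths" (8.4); 60% capture, standardized difference 0.339, two-sided alpha 0.20 and stated power 77% (8.7).

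- Evaluable: 258 × 0.60 = 154.8, which agrees with "we would have 155 evaluable patients, with 77 patients per arm".
- Power, t-test: noncentrality = 0.339 × √(77/2) = 2.10; normal critical value 1.28; Φ(2.10 − 1.28) ≈ 79%.
- Power, Wilcoxon (effective n = 77 × 3/π): 78% at 0.339, and 77% at the plan's worked example of 1/3.

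The stated 77% is therefore sound, and slightly conservative for the t-test. The weak points are the 60% input and how the values arise.

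**2. Capture rate.** The documents give only 60%, so other rates are assumptions. Power at 0.339, t-test (Wilcoxon):

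| Capture | Per arm | Power |
|---|---|---|
| 60% | 77 | 79% (78%) |
| 50% | 64 | 74% (72%) |
| 40% | 51 | 67% (65%) |
| 20% | 25 | 47% (46%) |

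**3. Selection, two-group illustration.** All inputs are assumed: no arm effect, 30% of patients worsening, their mean CTC 1 SD higher, 60% tested overall in each arm. The share of worsening patients among those tested is 0.30 × (their testing rate) / 0.60. The false difference in SD is Arm A's share minus Arm B's.

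| Worsening patients tested, A / B | Shares, A − B | False difference | Rejection (nominal 20%) |
|---|---|---|---|
| 90% / 90% | 0.45 − 0.45 | 0 | 20% |
| 80% / 60% | 0.40 − 0.30 | 0.10 SD | 28% |
| 90% / 60% | 0.45 − 0.30 | 0.15 SD | 38% |
| 90% / 40% | 0.45 − 0.20 | 0.25 SD | 61% |

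The last row has testing favor worsening patients in one arm and stable patients in the other, so it is an extreme. Equal overall capture does not protect the comparison; an equal testing pattern does.

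**4. Selection, simulated counts.** Assumed: overdispersed counts (log-normal Poisson, mean 1.2, SD 1.8), no arm effect, log-odds of being tested rising linearly with disease activity. The slope per SD of activity is set for each arm.

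| Tested, A / B | Slope, A / B | False difference (A − B) |
|---|---|---|
| 60% / 60% | 0.6 / 0 | 0.12 to 0.14 SD |
| 60% / 60% | 0.6 / 0.3 | 0.06 SD |
| 60% / 60% | 0.6 / 0.4 | 0.04 SD |
| 60% / 60% | 0.6 / 0.6 | 0 |
| 70% / 50% | 0.6 / 0 | 0.09 SD |
| 50% / 70% | 0.6 / 0 | 0.17 SD |
| 70% / 50% | 0.6 / 0.6 | about −0.07 SD |
| 50% / 70% | 0.6 / 0.6 | about +0.07 SD |

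The difference in slopes drives the result. Unequal testing rates add a smaller bias of either sign. At the strongly asymmetric end, 0.09/0.339 = 27% and 0.17/0.339 = 50% of the design effect; with 77 per arm, rejection rises from 20% to about 27% and 42%.

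**5. Candidate remedies under the simulation.** Weighting by the inverse probability of having a count removed about 27 to 75% of the bias at under 4% loss of effective sample size. Restricting to patients with a randomization count left the unweighted bias unchanged. At an assumed 50 per arm, restriction would cut power from 79% to about 66%.

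**The case against.** The strongest reply is that footnote 6 can work through site practice and insurance, which are largely settled before randomization. The test is scheduled for both arms at the same two times, not on suspicion of progression, and 8.3 balances assignment within institutions and their affiliates. Capture driven only by site and payer would be about equal in the two arms. It would then cost sample size and generalizability without biasing the arm contrast. This stands as a plausible reading, and it is why zero belongs in the range. It does not settle the matter, because footnote 6 does not limit capture to site and payer factors and 8.7 plans no check.

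A reader might go further and infer that the 6-month comparison rests on a clinician-selected subset and is biased. The documents do not support that: they do not show arm-dependent ordering, and neither the direction nor the size of a bias can be derived from them.

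A reader might also infer that no study assay exists. That is drawn from the tube and kit lists, and part of Section 9 was not available for review. Footnote 6 is enough to show how the counts arise.

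Section 8.7 does also compare the reduction from randomization, which uses a count taken before assignment. But that count falls under the same footnote, and the comparison still needs the selectively obtained 6-month value.

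Finally, CTC is absent from the endpoints in 8.2 and is tested at alpha 0.20. That lowers the priority but does not remove the gap.

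**Conclusion.** The gap is real and minor. CTC values depend on standard-care testing and reimbursement, and 8.7 analyzes those available as if capture carried no information. Under the assumptions above, the false arm difference runs from zero, with the same testing pattern in both arms, to roughly 0.1 to 0.2 SD with strongly different patterns, against a design effect of 0.339 SD. Opposite selection in the two arms could exceed that range. These are illustrations of sensitivity, not estimates for this trial. The plan's 155 patients and 77% power are arithmetically sound, given 60% capture. The point bears on objective 2.2.3 only.

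**What to change.** In 8.7:

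- Keep all randomized patients with a 6-month count in the arm comparison.
- Add an analysis weighting each by the inverse probability of having that count, given arm, the stratification factors, the randomization count where available (with a missing indicator), and the last disease status recorded before the draw. The 3-monthly follow-up in 7.1 supplies that status without new data collection.
- Report the proportion tested by arm.
- State in advance that the arm comparison in 2.2.3 will be read as exploratory if the weighted and unweighted results disagree.
- Use the subset with a randomization count only as a sensitivity analysis, since restriction costs power and does not by itself remove selection at 6 months.

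The cost is wording in 8.7, modest analysis work and slightly wider intervals. Weighting corrects only for recorded reasons for testing; selection on unrecorded reasons remains.
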